11.2. SECONDARY ANALYSIS

There is no secondary efficacy analysis planned for Part 1.

For Part 2, the following secondary analysis are planned.

11.2.1. CHANGE FROM BASELINE AT DAY 36 ON THE CLINICAL DEMENTIA RATING SCALE – SUM OF BOXES TOTAL SCORE

The secondary efficacy endpoint, CFB at Day 36 on the CDRS – Sum of Boxes, and will be analyzed and reported as described for the primary analysis in Section 11.1.

Also, the summary statistics will be tabulated for CDRS individual scores, sum of box total score and Global CDRS score by treatment groups and baseline AD severity stratifications.

11.2.2. RESPONDER ON THE CLINICAL DEMENTIA RATING SCALE AT DAYS 36 AND 104

A responder is defined as at least 1-point improvement from baseline on the Sum of Boxes score. The patients with missing data will be included in the denominator and treated as a non-responder.

The proportion of the responders between treatment groups will be tested using the Cochran Mantel-Haenszel (CMH) test, adjusting for randomization strata (MMSE \leq 20 and 21-24) and the common risk difference and the 95% CI will be presented.

Also, the number and percentages of responders over time will be tabulated by treatment groups and baseline AD severity stratifications.

The CDRS individual scores, sum of box total score, Global CDRS score and responder status will be listed as well.

11.2.3. CHANGE FROM BASELINE COGNITIVE DRUG RESEARCH SYSTEM BATTERY AT DAYS 36 AND 104

This endpoint is analyzed separately, and detail of analysis is described in CDR system battery SAP [5].

11.2.4. CHANGE FROM BASELINE MMSE TOTAL SCORE AT DAYS 36 AND 104

The secondary efficacy endpoint, CFB at Day 36 and Day 104 on the MMSE total score will be analyzed using MMRM with treatment group, visit, and treatment group by visit interaction as fixed effects and a corresponding MMSE total baseline score as a covariate. The LS mean difference, the 95% CI of the difference, and the p-value will be presented as well as the descriptive statistics.

Also, the summary statistics will be tabulated for MMSE score by treatment groups and baseline AD severity stratifications.

The MMSE scores will be listed as well.

11.2.5. CHANGE FROM BASELINE NPI TOTAL SCORE AT DAYS 36 AND 104

The secondary efficacy endpoint, CFB at Day 36 and Day 104 on the NPI total score will be analyzed using MMRM with treatment group, randomization strata (MMSE \leq 20 and 21-24), visit, and treatment group by visit interaction as fixed effects and a corresponding NPI total baseline score as a covariate. The LS mean difference, the 95% CI of the difference, and the p-value will be presented as well as the descriptive statistics.

Also, the summary statistics will be tabulated for NPI by treatment groups and baseline AD severity stratifications.

The individual and composite NPI scores will be listed as well.

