7.1.2. SAFETY ANALYSIS SET (SAS)

The Safety Analysis Set (SAS) includes all subjects in the FAS who received at least one dose of study drug. Subjects in this analysis set will be analyzed according to the study drug they actually received. The FAS and the SAS will be the same if all randomized patients are dosed with study drug. The SAS will be used for all analyses, except for disposition, protocol deviations, PK and PD.

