7.1.4. PHARMACODYNAMIC ANALYSIS SET (PDS)

The Pharmacodynamic Analysis Set (PDS) includes all subjects who received assigned dose of TB006 or placebo and have at least one post-dose evaluable PD assessment. The PDS will be used for all PD and efficacy analyses.

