11. EFFICACY PARAMETERS

All the efficacy analysis planned for Part 1 will be performed using PDS and efficacy analysis planned for Part 2 will be performed using EAS2. The EAS2 include all PDS subjects of Part 2, placebo subjects of Part 1 and subjects with same dose level in Part 1 pooled together.

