2. PURPOSE

The Statistical Analysis Plan (SAP) version 2.0 dated 11 April 2022 need to clarify the definition of Efficacy Analysis Set-Part 2 (EAS2). The EAS2 is defined in SAP as:

The Part 2 – Efficacy Analysis Set (EAS2) includes all subjects who received assigned dose of TB006 in Part 2 and the subjects enrolled at the same TB006 dose level in Part 1, as well as all placebo patients will be included and have at least one post-dose evaluable PD assessment across subject.

Here “PD assessment” can be mistaken to refer to plasma or imaging biomarkers and hence the definition for EAS2 is clarified in addendum SAP to replace text “PD” with text “efficacy”. The updated definition is as under:

The Part 2 – Efficacy Analysis Set (EAS2) includes all subjects who received assigned dose of TB006 in Part 2 and the subjects enrolled at the same TB006 dose level in Part 1, as well as all placebo patients will be included and have at least one post-dose evaluable **efficacy** assessment across subject.

3. DESCRIPTIONS OF CHANGES IN STUDY CONDUCT AND ANALYSIS PLANNED IN PROTOCOL AND STATISTICAL ANALYSIS PLAN

This change will only impact the analysis population definition in SAP version 2.0 dated 11 April 2022, Section 7.1.5.

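### Dosed patients with no efficacy assessment after dosing fall outside the Part 2 responder denominator, although the plan counts missing data as non-response

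*SAP*

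**What the plan says.** - **Responder (SAP 11.2.2).** "A responder is defined as at least 1-point improvement from baseline on the Sum of Boxes score".
- **Missing data.** SAP 11.2.2 then sets the scoring rule, which protocol 9.4.5 shares: "The patients with missing data will be included in the denominator and treated as a non-responder".
- **Set used.** SAP Section 11 states that "efficacy analysis planned for Part 2 will be performed using EAS2", and SAP Appendix II lists the Cochran-Mantel-Haenszel responder test on EAS2.
- **Who is in EAS2.** SAP 7.1.5, as reworded in Section 2 of the addendum, takes the Part 2 patients who received their assigned dose and the Part 1 patients at the same dose, and ends with this condition: "as well as all placebo patients will be included and have at least one post-dose evaluable". What must be evaluable is now an assessment of efficacy, where SAP 7.1.5 had said PD; the requirement for an assessment after dosing stayed.
- **Reach of the addendum (its Section 3).** "This change will only impact the analysis population definition in SAP version 2.0 dated 11 April 2022, Section 7.1.5".
- **Section 11, not amended.** "The EAS2 include all PDS subjects of Part 2, placebo subjects of Part 1 and subjects with same dose level in Part 1 pooled together". The PDS in SAP 7.1.4 still requires that patients "have at least one post-dose evaluable PD assessment".
- **Nothing wider is planned.** SAP 7.1.1 gives the all-randomised set only to disposition and deviations, and SAP 11.3 declares sensitivity analysis not applicable.

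**The concern.** Scoring missing data as non-response keeps early loss from improving a response rate. It can act only on patients who are in the analysis set. A dosed patient with no efficacy data at all after dosing has the most complete form of missing data, yet the entry condition of EAS2 removes that patient before the rule applies.

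The outcome then depends on an administrative detail. Two patients may stop after the first infusion for the same reason. The one who attends an E/D visit is a non-responder in the denominator; the one who does not is absent from it. Protocol Section 7 asks for the E/D visit only where it is possible. At stake is a small upward shift in each arm's response rate and, if the arms lose different numbers this way, a biased difference on a secondary endpoint.

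**Working it through.** **1. Who is lost.** In the Part 2 schedule (protocol Table 2), the first efficacy test after dosing is the Cognitive Drug Research battery on Day 8; the first Clinical Dementia Rating after dosing is on Day 15. The E/D visit includes the Clinical Dementia Rating, MMSE, NPI and the battery. SAP 6.2 lists the battery among the Part 2 efficacy endpoints. So:

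| Dosed patient | In EAS2 (7.1.5 as amended)? | Responder status |
|---|---|---|
| Leaves early, has an E/D visit | Yes | Non-responder if the score for that day is missing |
| Has the Day 8 battery, then leaves | Yes | Non-responder |
| Leaves before Day 8, no E/D or later assessment | No | Not counted |

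Only the last row escapes the rule in SAP 11.2.2.

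**2. The plan's own figure.** SAP 6.1.1 gives about 64 per arm: 58 from Part 2 plus 6 from Part 1. With a difference of 0.25, SD 0.5 and two-sided 5%, the exact t-test calculation gives 80.1% power at 64 per arm, so the stated total of 128 reproduces. It concerns the primary endpoint. No rate, power or sample size is stated for the responder endpoint.

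**3. One arm.** With *r* responders and *e* excluded patients, the rate is *r*/(64 − *e*) instead of *r*/64, an inflation of 64/(64 − *e*). Assume *r* = 16:

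| *e* | Rate |
|---|---|
| 0 | 16/64 = 25.0% |
| 1 | 16/63 = 25.4% |
| 2 | 16/62 = 25.8% |
| 4 | 16/60 = 26.7% |
| 6 | 16/58 = 27.6% |

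**4. The treatment difference.** All responder counts and exclusions here are assumed.

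| Responders, TB006 v placebo | Excluded, TB006/placebo | Rates | Difference (points) |
|---|---|---|---|
| 16 v 16 | 6/6 | 27.6% v 27.6% | 0 |
| 16 v 16 | 6/0 | 27.6% v 25.0% | 2.6 |
| 16 v 8 | 0/0 | 25.0% v 12.5% | 12.5 |
| 16 v 8 | 1/1 | 25.4% v 12.7% | 12.7 |
| 16 v 8 | 3/1 | 26.2% v 12.7% | 13.5 |
| 16 v 8 | 6/2 | 27.6% v 12.9% | 14.7 |

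Equal exclusions create no difference where the arms respond equally; where they do not, they stretch the difference slightly. Unequal exclusions can create one. For 16 v 8, an unstratified chi-square test (not the planned stratified test) gives p = 0.0700 with no exclusions, 0.0566 with 3/1 and 0.0445 with 6/2. The last row needs 6/64 = 9.4% of one arm to leave in the first week without an exit assessment, which sits badly with the few withdrawals that the protocol expects.

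**The case against.** The best defence is that there is no contradiction: EAS2 is the set, and SAP 11.2.2 says how missing values are scored inside it. The text does not say every randomised or dosed patient. Requiring an assessment after dosing is an open choice, already made in protocol 9.3, which uses the PDS for efficacy. The protocol also asks sites to hold an E/D visit where they can and to keep visits going to Day 104. This stands in part: the two provisions can be applied together, and few patients should be affected. It does not explain why total absence of data should be treated more leniently than partial absence.

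Some stronger readings are tempting but not supported:

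- *All early leavers vanish and the non-responder rule is defeated.* No. An E/D visit or a Day 8 battery keeps a patient in, and the rule works for all later missing data.
- *Section 11 sets up a second population, losing patients up to Day 36 and giving the primary MMRM two populations.* This requires PD to mean biomarkers only, for which the first scheduled blood sample after dosing is on Day 36. The schedules list cognition testing under pharmacodynamic assessments, protocol 8.6 does the same, and the addendum calls the biomarker reading a mistake. Read that way, Section 11 and 7.1.5 nearly agree for Part 2 patients. The addendum changed 7.1.5; it did not withdraw the PDS. For the case shown here, a patient with no Sum of Boxes score after baseline gives the MMRM no outcome in any event.
- *Efficacy belongs on the safety set.* SAP 7.1.2 does say "The SAS will be used for all analyses, except for disposition, protocol deviations, PK and PD", without naming efficacy, but 7.1.5, Section 11 and Appendix II assign Part 2 efficacy specifically to EAS2.
- *The lost patients are tolerability losses on active drug.* Plausible, but neither document says so.

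**Conclusion.** The point holds in a limited form. Dosed patients who leave before the Day 8 battery with no E/D or later assessment are excluded from the responder denominator instead of being counted as non-responders, and no other planned analysis puts them back. On the illustrative 16 of 64, the arm's rate rises by 0.8 points with 2 exclusions and 1.7 points with 4. The true size cannot be computed, because the documents give neither a dropout nor a responder rate; it is probably small. The direction of any bias in the treatment comparison is unknown and depends mainly on whether exclusions differ by arm. The endpoint is secondary. This is an inexpensive improvement that makes the plan's own rule work fully; it does not show that the responder or primary analysis is invalid. The leftover PDS wording in Section 11 is a matter of alignment only.

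**What to change.** Add one paragraph to the SAP by addendum before database lock:

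1. For the Day 36 and Day 104 responder analyses, take as denominator all randomised and dosed patients in the pooled set (Part 2, Part 1 at the same dose, and all placebo), with no condition on assessments after dosing. Patients without the relevant Sum of Boxes score are non-responders, as SAP 11.2.2 already says. The stratified test and the risk difference stay as planned.
2. In Section 11, replace the description of EAS2 through the PDS with a reference to 7.1.5 as amended, so that the biomarker misreading named in the addendum cannot return. This also removes a small mismatch: Section 11 states no post-dose condition for Part 1 patients, while 7.1.5 does.

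No new data are needed. The costs are a slightly lower reported response rate and a responder denominator that can differ from the MMRM set, which a table footnote should state.

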11.3. SENSITIVITY ANALYSIS

Not applicable for either part of this study.

[REDACTED]

[REDACTED]

11.4.1. CHANGE FROM BASELINE THROUGH END OF STUDY – COGNITION PARAMETERS

The observed and change/shift from baseline in results from the cognition parameters - CDRS individual scores, sum of box total score, Global CDRS score, Responders for CDRS-sum of boxes total score, MMSE score, and NPI total score will be summarized by treatment groups using continuous and categorical descriptive statistics.

The assessment associated with cognition parameters - CDR system battery, will be analyzed separately, and detail of analysis is described in CDR system battery SAP [5].

11.5. INTERIM ANALYSIS

No formal interim analysis planned for this study.

A SRC will meet for each dose cohort before continuing to the next dose cohort.

11.6. SUBGROUP ANALYSES

The subgroup analysis for Part 2 will be performed as described in Section 7.2.

12.SAFETY AND TOLERABILITY

12.1. ADVERSE EVENTS

The following AE definitions are applicable to both protocol parts of this study:

- AE reporting period: Defined from start of first dose of study drug infusion on Day 1 up to and including End of Study.
- AE: Any untoward medical occurrence in a subject.
- Treatment-emergent AE (TEAE): Defined as any AE that started on or after first dose of study drug infusion within the studies' AE reporting period.
- SAE: Defined as any AE that is indicated as serious on the AEs Details eCRF, as per investigator's assessment.
- Related AE: Defined as any AE that is indicated as related to study drug on the AEs Details eCRF, as per investigator's assessment.
- AE leading to discontinuation: Defined as any AE that has an "other action taken" indicated as "withdrawn from study" on the AEs Details eCRF.

All AEs will be coded using the MedDRA version 22.1, Sep 2019. The following AE items will be listed separately for each protocol parts using the SAS:

- All AEs
- AEs leading to study discontinuation
- Serious AEs
- AEs leading to death (if applicable)

The following items are planned to be presented in summary tables showing event incidence and corresponding subject count, experiencing said AE/AE type using the SAS, by treatment groups using SAS:

- AE overview, including row items for frequency of subjects [n(%)] experiencing:
 - At least one AE
 - AEs by toxicity grade
 - Grade 1
 - Grade 2
 - Grade 3
 - Grade 4
 - Grade 5
 - Serious AEs

- Related AEs
- Non-related AEs
- AEs leading to study discontinuation
- AEs leading to death
- AEs by system organ class (SOC) and preferred term (PT)
- AEs by descending incidence of PT
- AEs by toxicity grade (Common Terminology Criteria for Adverse Events [CTCAE] grading)
- Related AEs by SOC and PT
- Related AEs by descending incidence of PT.
- Serious AEs
- AEs resulting in death
- AEs leading to study discontinuation

Only TEAEs will be used for summarization of all tables, but for listing all AEs will be counted. The TEAE status will be derived using the AE start and stop dates as per definition provided at the start of this section. For partial dates see [Section 9.4.1](#).

The data for these presentations will be obtained from the Adverse Events Details eCRF.

AE assignment to CTCAE toxicity grades is explained in [Table 2](#) below.

Table 2. CTCAE Grades

Grade	Grade Description	Grade Details
Grade 1	Mild	Asymptomatic or mild symptoms; clinical or diagnostic observations only; intervention not indicated
Grade 2	Moderate	Minimal, local, or non-invasive intervention indicated, limiting age-appropriate instrumental ADL*
Grade 3	Severe	Severe or medically significant but not immediately life-threatening; hospitalization or prolongation of hospitalization indicated; disabling; limiting selfcare ADL*
Grade 4	Life-threatening	Life-threatening consequences: urgent intervention indicated
Grade 5	Fatal	Death related to AE

ADL: activities of daily living.
*Instrumental ADL refer to preparing meals, shopping for groceries or clothes, using the telephone, managing money, etc.
** Self-care ADL refer to bathing, dressing, and undressing, feeding self, using the toilet, taking medications, and not bedridden.

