8.3.4 Regulatory Reporting Requirements for Serious Adverse Events

- Notification by the investigator to the sponsor of an SAE is essential so that legal obligations and ethical responsibilities towards the safety of patients and the safety of a study drug under clinical investigation are met.
- The sponsor has a legal responsibility to notify the FDA about new safety information of a study drug under clinical investigation. The sponsor will comply with regulatory requirements relating to safety reporting to the FDA, IRB/IEC, and investigators.
- Investigator safety reports must be prepared for SUSARs according to local regulatory requirements and sponsor policy and forwarded to investigators as necessary.
- An investigator who receives an investigator safety report describing an SAE or other specific safety information (eg, summary or listing of SAEs) from the sponsor will review and then file it along with the IB and will notify the IRB/IEC, if appropriate according to local requirements.

8.3.5 Disease-related Events and/or Disease-related Outcomes not Qualifying as Adverse Events or Serious Adverse Events

The following DREs are common in patients with AD and can be serious/life threatening:

- Anxiety and psychosis
- Dysphagia and other eating disorders
- Exacerbation of AD
- Injuries from falls

Because these events are typically associated with the disease under study, they will not be reported according to the standard process for expedited reporting of SAEs even though the event may meet the definition of an SAE. These events will be recorded in the patient's CRF when reported. These DREs will be monitored by the SRC on a routine basis.

NOTE: However, if either of the following conditions applies, then the event must be recorded and reported as an SAE (instead of a DRE):

• The event is, in the investigator's opinion, of greater severity, frequency, or duration than expected for the individual patient.

OR

Protocol TB006AD2102

Protocol Date and Version: 15 Oct 2021; v 3.0

• The investigator considers that there is a reasonable possibility that the event was related to study drug.

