9.4.2 Part 1 Primary Endpoints

9.4.2.1 Safety and Tolerability

All AEs will be coded using the most recent version of MedDRA. The incidence of AEs will be summarized by SOC and PT. Similar summaries will be produced for AEs by severity, SAEs, treatment related AEs, and AEs leading to discontinuation. AEs are collected from the first dose of study drug, thus all AEs are considered treatment emergent AEs.

The ECG results will be presented by visit, summarizing the continuous measurements based on the average of triplicate values, including the QT, QTc, QRS, RR, PR intervals, as well as change from baseline values, and clinically significant changes in heart rate and rhythm.

Reported values and change from baseline values of hematology, clinical chemistry and urinalysis (and the determinations relevant to the normal ranges and appropriate clinically significant or CTCAE toxicity gradings) will be summarized by laboratory test for each assessment day, using appropriate descriptive statistics.

Vital signs (systolic and diastolic blood pressure, pulse rate, respiratory rate, and oral temperature) will be summarized by assessment day showing absolute values, change from baseline values, and clinically significant changes (including orthostasis) using appropriate descriptive statistics.

Physical and neurological examinations will be summarized by assessment day showing shift from baseline.

Protocol TB006AD2102

Protocol Date and Version: 15 Oct 2021; v 3.0

The C-SSRS assessments will be presented in a by-subject listing.

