- Grade 3: Severe or medically significant but not immediately life-threatening; hospitalization or prolongation of hospitalization indicated; disabling; limiting self-care ADL (eg, bathing, dressing and undressing, feeding self, using the toilet, taking medications).
 - An AE that is assessed as severe should not be confused with an SAE. Severe is a category utilized for rating the severity of an event; and both AEs and SAEs can be assessed as severe. An event is defined as 'serious' when it meets at least 1 of the predefined outcomes as described in the definition of an SAE, NOT when it is rated as severe.
- Grade 4: Life-threatening consequences; urgent intervention indicated.
- Grade 5: Death related to AE.

Assessment of Causality

- The investigator is obligated to assess the relationship between study drug and each occurrence of each AE/SAE.
- A "reasonable possibility" of a relationship conveys that there are facts, evidence, and/or
 arguments to suggest a causal relationship, rather than that a relationship cannot be ruled
 out.
- The investigator will use clinical judgment to determine the relationship.
- Alternative causes, such as underlying disease(s), concomitant therapy, and other risk
 factors, as well as the temporal relationship of the event to study drug administration, will
 be considered and investigated.
- The investigator will also consult the IB in his/her assessment.
- For each AE/SAE, the investigator must document in the medical notes that he/she has reviewed the AE/SAE and has provided an assessment of causality.
- There may be situations in which an SAE has occurred and the investigator has minimal
 information to include in the initial report. However, it is very important that the
 investigator always makes an assessment of causality for every event before the initial
 transmission of the SAE data.

Protocol TB006AD2102

Protocol Date and Version: 15 Oct 2021; v 3.0

 The investigator may change his/her opinion of causality in light of follow-up information and send an SAE follow-up report with the updated causality assessment.

- The causality assessment is one of the criteria used when determining regulatory reporting requirements.
- Causality assessments are defined below:
 - Causality assessments that indicate the event is "Not Drug Related":
 - Unrelated: The event is related to an etiology other than the study drug administration (the alternative etiology must be documented in the patient's medical record).

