13.2. PHYSICAL AND NEUROLOGICAL EXAMINATIONS

A listing of physical and neurological examination findings for both protocol parts will be presented separately using the SAS.

The information for the listing will be obtained from the following eCRFs:

- Physical and Neurological Examination
- Physical and Neurological Exam Abnormalities

It should be noted that weight will be presented and summarized alongside the vital signs (see Section 12.4 for details), and height will be presented alongside demographics and baseline characteristics (see Section 10.2 for details).

Body systems to assess include:

-
- Cardiovascular
 - Respiratory
 - Gastrointestinal
 - Neurological (Mental status, Motor and Sensory Skills, Hearing and Speech, Vision, Coordination, Balance)

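### Disease-related events that are neither escalated to SAE nor entered on the adverse event form have no planned listing or by-arm table, so an excess on TB006 could go unreported

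*SAP*

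**What the plan says.** **Protocol 8.3.5** is headed "Disease-related Events and/or Disease-related Outcomes not Qualifying as Adverse Events or Serious Adverse Events". It lists anxiety and psychosis, dysphagia and other eating disorders, exacerbation of AD, and "Injuries from falls". The body text says that such events "will not be reported according to the standard process for expedited reporting of SAEs even though the event may meet the definition of an SAE". They are to be recorded in the CRF, with no form named, and followed routinely by the Safety Review Committee (SRC). A note adds an exit: if the investigator finds the event worse, more frequent or longer than expected for that patient, or possibly drug-related, "then the event must be recorded and reported as an SAE (instead of a DRE").

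**Protocol 10.2.1 and 10.2.2** leave expected progression and symptoms of the disease outside the AE definition, say that an event that is not an AE cannot be an SAE, and define an SAE by outcome criteria.

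**SAP 12.1** lists the adverse event outputs and gives their source: "The data for these presentations will be obtained from the Adverse Events Details eCRF". DREs appear nowhere in the SAP.

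**Examinations.** Protocol 9.4.2.1, under Part 1, says: "Physical and neurological examinations will be summarized by assessment day showing shift from baseline". SAP 13.2 says: "A listing of physical and neurological examination findings for both protocol parts will be presented separately using the SAS". SAP section 8, which is the place for departures from the protocol, declares only the dose-proportionality assessment.

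**The concern.** In a placebo-controlled trial, an investigator looking at one blinded patient cannot tell whether an ordinary fall or a swallowing problem is part of AD or an effect of the drug. Only a comparison of frequencies between arms can. The DRE category takes exactly these events out of the AE definition, and the SAP gives them no table to land in. Protocol 2.3.1 calls TB006 first in class with no known class effects, so investigators also have little to base attribution on.

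The exit from the category raises the opposite problem. Taken literally, the note sends a non-serious event straight to SAE status, with no route to a non-serious AE. The AE incidence endpoint could then be too low while the SAE count includes events that meet no seriousness criterion.

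**Working it through.** The documents state no DRE rate, so there is no figure of the plan's to reproduce. The check is mainly a reading of the DRE rules against every safety output.

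**Step 1: where a DRE can go.** Under 8.3.5 there are three possibilities.
- It is escalated to SAE. It then enters the SAP 12.1 outputs.
- It is not escalated, but the site enters it on the AE Details form. SAP 12.1 defines an AE broadly and does not exclude disease-related events, so it is tabulated.
- It is not escalated and is recorded elsewhere in the CRF. It is then in no SAP 12.1 output.

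**Step 2: is there any other output for the third route?**
- SAP 6.3 (safety endpoints) has no DRE item.
- SAP 12.2 to 12.5 cover laboratory tests, ECG, vital signs and the C-SSRS.
- SAP 13.1 lists hospitalizations, but takes them from the AE Details form as well.
- SAP 13.2 lists examination findings, and 13.3 covers antibodies.

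None lists or tabulates DREs.

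**Step 3: does monitoring fill the gap?** Protocol 8.3.5 names the SRC. The synopsis gives the committee as Part 1 only, and section 9.6 describes it as blinded. No comparison by arm is assigned to anyone for Part 2, where the 58-versus-58 comparison lies.

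**Step 4: size, for illustration only.** Assume that 10% of placebo and 25% of TB006 patients have a DRE, with 58 per arm (protocol 4.1.2). Let f be the share that reaches the AE Details form, by escalation or direct entry, equal in both arms.

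True excess = 58 × 0.25 − 58 × 0.10 = 14.5 − 5.8 = 8.7 patients. Visible excess = 8.7 × f; hidden excess = 8.7 × (1 − f).

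| f | Placebo visible | TB006 visible | Visible excess | Hidden excess |
|---|---|---|---|---|
| 0 | 0 | 0 | 0 | 8.7 |
| 10% | 0.58 | 1.45 | 0.87 | 7.83 |
| 25% | 1.45 | 3.625 | 2.175 | 6.525 |
| 50% | 2.9 | 7.25 | 4.35 | 4.35 |
| 100% | 5.8 | 14.5 | 8.7 | 0 |

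The excess is wholly hidden only at f = 0, that is, with no escalation and no AE-form entry. The rates and f are assumptions.

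**Step 5: the note against 10.2.** The first condition of the note includes greater severity than expected and the second is possible relatedness. Neither is a seriousness criterion in 10.2.2. Section 10.2.3 keeps the two ideas apart: "An AE that is assessed as severe should not be confused with an SAE". A mild anxiety episode judged possibly related meets the note and meets nothing in 10.2.2.

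**Step 6: examinations.** Protocol 9.4.2.1 plans a shift summary by day; SAP 13.2 plans a listing; SAP section 8 is silent. This is certain for Part 1. For Part 2, protocol 9.4.5 points to itself for how safety results are presented, so the intended summary there is unclear.

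**The case against.** **The AE tables may catch these events.** The heading of 8.3.5 is broad, but its body waives only expedited reporting. The SAP's AE definition would admit a DRE entered on the AE Details form, and which form sites use depends on the eCRF specification that the SAP cites and that is not among these documents. Escalated events are tabulated too. This stands. A reader might infer that a TB006 excess would be absent from the safety results altogether; the documents support only that the non-escalated part, kept off that form, has no planned output.

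**Other by-arm outputs exist.** The NPI rates delusions, hallucinations and anxiety, and its total is modelled by arm. Sum of Boxes, the primary endpoint, measures AD worsening. Concomitant medications and reasons for discontinuation are tabulated by arm. This stands in part: the four categories are not equally exposed. But these scales are efficacy results, none of the 10 NPI domains is eating (protocol 8.6.3.4), and neither scale records falls injuries.

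**CNS safety does not rest on the examination alone.** The C-SSRS is scheduled at dosing and follow-up visits, and SAP 12.5 tabulates it by arm, which is more than the listing in protocol 9.4.2.1. A reader might take the neurological examination to be the only other scheduled measure; it is not. The shift-table mismatch remains, but is minor and separate.

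**The note can be read more narrowly.** It follows text on events that may meet the SAE definition, so it may be meant to restore SAE reporting for those only, and SAP 12.1 takes SAE status from the investigator's seriousness entry. That is a plausible intention, but the note does not say so, and a site following its words would record a non-serious event as an SAE.

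**Conclusion.** The point holds in limited form, with medium confidence.

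DREs that are not escalated and not on the AE Details form have no planned listing or by-arm table in either part. The exposure is greatest for falls injuries and dysphagia. How much is lost cannot be determined from the documents: it depends on the true rates, on the share escalated, and on which CRF form sites use. In the illustration it ranges from 0 to 8.7 excess patients out of 58. Adding the tables is a cheap improvement rather than the correction of a proven loss.

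Two items are wrong as written. The 8.3.5 note gives SAE status without a seriousness condition, in conflict with 10.2.2. SAP 13.2 drops the Part 1 examination shift summary without declaring it in SAP section 8.

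**What to change.** 1. State which CRF form holds DREs. Add to SAP 12.1, for each part on the safety set: a DRE listing; a by-arm table of patients and events in the four categories; and a combined AE-plus-DRE table by SOC and PT. State in SAP 12.1 how its AE definition relates to protocol 8.3.5 and 10.2.1.
2. Reconcile the 8.3.5 note with 10.2.1 and 10.2.2, so that an event leaving the DRE category is counted as an SAE only if it meets the SAE definition, and otherwise as an AE.
3. Restore the by-arm examination shift table in SAP 13.2.

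**Cost.** Table programming, MedDRA coding of DREs (the documents do not say that they are coded), and one reworded protocol note. No new patient assessments are needed, because 8.3.5 already requires DREs to be recorded in the CRF. The SAP has already been clarified once by addendum, so that route is available for items 1 and 3.
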